2.4 Data Conventions

Unless stated otherwise in specific subsequent sections, data conventions and definitions listed below will be applied to all analyses.

- Day 1 is defined as the day when the patient receives the 1st study treatment. Study day = visit date – date of the 1st study treatment + 1
- For patients who were randomized but did not receive any study treatments after randomization, the date of randomization will be used as Day 1.

Study duration will be calculated for each patient as:
Study duration for the primary DBL = date of the Week 52 visit (or early exit if discontinued before the primary DBL) – date of the 1st study treatment + 1

Study duration for the final DBL = date of the Week 104 visit (or early exit) – date of the 1^{st} study treatment + 1

- Unless otherwise specified, baseline data refer to assessments performed at the Baseline (Day 1) visit prior to the 1st study treatment. Screening or unscheduled visits prior to Day 1 visit will be used for baseline in the absence of pertinent data at the baseline visit.
- If ungradable images result in missing baseline CRT, the manual read data for retinal thickness at the center point, if available, will be used for analysis. If the manual read data at baseline is not available, CRT on confirmation reading at screening will serve as baseline CRT.
- Descriptive statistics include the sample size (N), mean, standard deviation (SD), median, minimum (Min), and maximum (Max) for continuous/ordinal data and the frequency distribution includes sample size (N), frequency count, and percentage for categorical data.
- The difference between groups will be calculated as abicipar minus ranibizumab.
- Medical Dictionary of Regulatory Activities (MedDRA) nomenclature will be used to code adverse events, medical procedures, biomicroscopy, and ophthalmoscopy findings.
- The Anatomical-Therapeutic-Chemical classification text from World Health Organization (WHO) Drug Dictionary will be used to code all medications for drug class and for drug name.
- Whenever applicable, the metric system will be used (eg, kilograms [kg] and centimeters [cm]) and all clinical laboratory data will be presented with the Standard International (SI) units.
- **3.** Disposition and Exit Status
- 3.1 Disposition and Exit Status

Patient disposition will be summarized as a frequency distribution by treatment group using the ITT and PP populations. For the Week 52 analysis, patients who are still in the study will

be classified into the ongoing category. Reasons for early exit will be summarized into the following categories as captured on the study exit eCRF.

3.2 Significant Protocol Deviations

Significant protocol deviations will be classified based on the type of deviation for each treatment group. Summary of significant protocol deviations will be done for the ITT population.

4. Demographics and Other Baseline Characteristics

4.1 Demographics

Demographic data are collected at the screening visit. Patient's age (years), sex, and race will be summarized for each treatment group using the ITT and PP populations. Patient age will be classified into categories of less than or equal to 65 years and greater than 65 years.

4.2 Baseline Characteristics

Baseline characteristics include height (cm), weight (kg), iris color, lesion type (predominantly classic, minimally classic, or occult), lesion size, subretinal or intraretinal fluid, intraretinal cysts, pigment epithelial detachments, polypoidal choroidal vasculopathy, and smoking status. Ocular characteristics of the study eye at baseline include lens status, study eye as the better-seeing eye (defined as baseline $BCVA_{study-eye} > BCVA_{non-study eye}$), BCVA, CRT, and intraocular pressure. Summaries of baseline characteristics will be done for the ITT and PP populations.

4.3 Prior Medications/Procedures

Prior medications are defined as those received prior to the first study treatment. For analysis purposes, a medication will be considered as a prior medication if it satisfies at least one of the following:

- The start date is prior to Day 1, regardless of the stop date;
- The start date is unknown but marked as > 1 year; or
- The stop date is prior to or on Day 1, regardless of the start date

For medications with a partial start or stop date where > 1 year is not marked for the start date or ongoing is not marked for the stop date and the day and/or the month is unknown, comparison to the 1st study treatment date (Day 1) will start with the year followed by the month, if applicable, for determination of prior medications. In cases where a full determination cannot be made based on the partial information, the start date will be assigned to the 1st day of the month if the day of the month is missing or to January if the month of the year is missing; conversely, the stop date will be assigned to the last day of the month if the day of the month is missing or to December if the month is missing. This missing data imputation will only be used to determine whether a certain medication is considered a prior medication. Prior medications will be summarized by treatment group under each drug class and drug name. A separate analysis for prior ophthalmic medications used in the study eye will be performed based on WHODDE base preferred names.

Summary of prior medications will be based on the ITT population.

4.4 Concomitant Medications/Procedures

Concomitant medications are defined as those non-study medications received after the first study treatment. For analysis purposes, a medication will be considered as concomitant if it satisfies at least one of the following:

- The start date is on or after the Day 1 treatment date regardless of the stop date;
- The stop date is after the Day 1 treatment date, regardless of the start date; or
- The stop date is unknown but marked as ongoing

For medications with a partial start or stop date, the same conventions and algorithms as described for prior medications will be used for determination of concomitant medications.

Concomitant medications will be summarized in the same way as prior medications.

Concurrent procedures including those ocular and nonocular procedures performed after study treatment will be coded using MedDRA. The number and percentage of patients with any concurrent procedures will be tabulated and presented by treatment group as a frequency distribution for each primary system organ class (SOC) and preferred term. A separate summary for ocular concurrent procedures in the study eye will be performed.

The number and percentage of patients who escaped to standard-of-care will be tabulated by medication names for each treatment group.

Summary of concomitant medications/procedures will be based on the ITT population.

4.5 Medical History

Medical history will be coded using MedDRA.

Data will be summarized by frequency distribution for each unique primary SOC and preferred terms using the ITT population based on the following two categories:

- Previous medical conditions, and
- Medical conditions at study initiation

Further, ocular history for the study eye will be summarized similarly.

5. Efficacy Analyses

The primary and secondary efficacy endpoints are listed below.

Primary efficacy endpoint:

• The proportion of patients with stable vision (ie, patients who lose fewer than 15 letters in BCVA) from baseline at Week 52

Secondary efficacy endpoints:

- Mean change from baseline in BCVA at Week 52 (key secondary endpoint)
- Mean change from baseline in CRT as assessed with SD-OCT and quantified by the central reading center at Week 52
- Proportion of patients with a gain of 15 or more ETDRS letters in BCVA from baseline at Week 52
- Mean change from baseline in The National Eye Institute Visual Function Questionnaire-25 (NEI-VFQ-25) composite score at Week 52

Analyses of the primary efficacy endpoint and the key secondary endpoint for testing noninferiority will be performed using the PP population. Analyses of the primary and secondary efficacy endpoints for testing superiority will be performed using the ITT population.

5.1 Collection of Primary Efficacy Measurement and Derivation of Primary Efficacy Variable

BCVA will be recorded on the CRF as the number of letters correctly read. For a given eye, the 4-meter distance (standard) of BCVA is tested first. If the patient correctly reads at least 20 letters at 4 meters, BCVA score will be set as the sum of 30 and the number of letters read correctly. If the patient correctly reads less than 20 letters at 4 meters, the BCVA is measured again at 1 meter. The BCVA score will be set to the number of letters read correctly at 1 meter plus the number of letters read correctly at 4 meters. For each patient, BCVA data will be collected for both eyes at the screening, baseline visit (Day 1 but prior to the study treatment), and at Weeks 12, 24, 36, 52, 76, and 104/early exit visits; and for the study eye only at all other scheduled visits.

For patients who received any non-study anti-vascular endothelial growth factor (VEGF) treatments in the study eye, data after the 1st such treatment will be excluded from all efficacy analyses.

5.2 Primary Efficacy Analyses

The primary efficacy endpoint is the proportion of patients with stable vision at Week 52, defined as vision loss of fewer than 15 letters in BCVA from baseline. Patients who escaped to standard of care by meeting the protocol criteria will be set to failures for the primary endpoint of stable vision at Week 52. Confirmation for meeting the protocol criteria is based on the marked reasons captured on the Standard of Care eCRF, which states: "Loss of \geq 30 letters in BCVA from baseline (in any post-baseline visit), and persistent fluid (subretinal and intraretinal) by OCT, judged to be the cause of the BCVA loss (not explained by reasons other than the progression of neovascular AMD)."

5.2.1 Statistical Hypothesis

The statistical hypothesis for testing non-inferiority of abicipar to ranibizumab with regard to stable vision at Week 52 can be stated as follows:

Null hypothesis:

Abicipar (2Q12 or 2Q8) is inferior to ranibizumab by the specified non-inferiority margin of 10% or more in the proportion of patients with stable vision at Week 52.

Alternative hypothesis:

Abicipar (2Q12 or 2Q8) is inferior to ranibizumab by less than the specified non-inferiority margin of 10% or is superior to ranibizumab in the proportion of patients with stable vision at Week 52.

The null and alternative hypotheses can be mathematically stated as follows:

 $H_{o1}: P_{2Q8} - P_{rQ4} \le -10\%$ $H_{a1}: P_{2Q8} - P_{rQ4} > -10\%$ And $H_{o2}: P_{2Q12} - P_{rQ4} \le -10\%$ $H_{a2}: P_{2Q12} - P_{rQ4} > -10\%$

where P_{2Q8} , P_{2Q12} , and P_{rQ4} are the probabilities of stable vision at Week 52 for the abicipar 2Q8, abicipar 2Q12, and ranibizumab treatment groups, respectively.

5.2.2 Primary Analyses of Primary Efficacy Variable

The primary analysis of the primary efficacy variable will be performed using the PP population based on a stratified method with Cochran-Mantel-Haenszel (CMH) weights. Within the framework of this method, the difference in the proportions between each abicipar arm and ranibizumab (abicipar group minus ranibizumab group) and the corresponding 2-sided 95.1% confidence interval for non-inferiority testing will be calculated. Specifically, the confidence intervals for treatment group differences will be calculated using the CMH weighted method with the baseline BCVA (\leq 55 versus > 55 ETDRS letters) as a stratification factor as described in Yan and Su (2010). Missing data for BCVA will be imputed using the last observation carried forward (LOCF). The formal non-inferiority test will be performed at Week 52 with a non-inferiority margin of 10% at an alpha level of 0.049. This alpha reflects an adjustment of 0.001 for the unmasked data review by the data safety monitoring committee (DSMC) for safety assessments. The total alpha spent of 0.001 for the DSMC is based on the assumption of no more than 10 unmasked reviews during the study, with 0.0001 allocated to each review. Thus, the overall alpha for the study is preserved at 0.05 level.

For hypothesis testing, if the lower limit of the 95.1% confidence interval for the difference between an abicipar group and ranibizumab is greater than or equal to -10%, non-inferiority of the abicipar group is established.

Multiplicity for the primary efficacy analysis will be controlled using a gatekeeping procedure defined by the following sequence to control the overall type I error rate at 0.05 level:

- **Step 1:** Testing for non-inferiority of abicipar 2Q8 against ranibizumab
- **Step 2:** Testing for non-inferiority of abicipar 2Q12 against ranibizumab

Hypothesis testing for abicipar 2Q12 against ranibizumab is valid only if non-inferiority for abicipar 2Q8 against ranibizumab is established.

If both abicipar groups have demonstrated non-inferiority to ranibizumab using the PP population, hypothesis testing for superiority will be performed using the ITT population for each abicipar group following the same order as defined above for non-inferiority testing. Superiority of abicipar will be demonstrated if the lower confidence limit for the treatment difference is greater than zero.

5.3 Secondary Efficacy Analyses

The key secondary efficacy variable is the mean change in BCVA from baseline. Other secondary efficacy variables include the mean change from baseline in CRT as assessed by SD-OCT, proportion of patients with BCVA improvement of 15 letters or more from baseline, and mean change from baseline in Health Outcomes NEI-VFQ-25 composite score.

5.3.1 BCVA Mean Change from Baseline

For the key secondary efficacy endpoint mean change from baseline in BCVA at Week 52, statistical analysis for non-inferiority will be based on the PP population using a mixed-effect model for repeated measures (MMRM), which includes BCVA data from baseline (Day 1) to Week 52. The model will include treatment group, region, baseline BCVA in the study eye, baseline CRT ($\leq 400 \ \mu m \ or > 400 \ \mu m$) in the study eye, lesion type of choroidal neovascularization (predominantly classic versus minimally classic or occult) from the confirmation at screening, visit, visit-by-baseline BCVA interaction, and treatment-by-visit interaction as fixed covariates using an unstructured covariance matrix. The difference in

BCVA mean change from baseline between each abicipar arm and ranibizumab (abicipar group minus ranibizumab group) and the corresponding 2-sided 95.1% confidence interval (CI) will be calculated based on the MMRM model. The formal non-inferiority test will be performed at Week 52 using a margin of 5 letters. Non-inferiority of abicipar will be established if the lower limit of the CI is > -5.0 letters. Testing for non-inferiority in mean change will also be performed using the ITT population and the same MMRM model as a sensitivity analysis.

Testing for superiority of abicipar over ranibizumab in BCVA mean change will be performed using the ITT population with the same MMRM model.

As a sensitivity analysis, BCVA mean change will be analyzed using an analysis of covariance (ANCOVA) model, which includes the treatment group, region, baseline CRT ($\leq 400 \text{ or} > 400 \text{ microns}$), and lesion type of choroidal neovascularization (predominantly classic versus minimally classic or occult) from the confirmation at screening as fixed effects and baseline BCVA as a covariate. In this model, missing data will be replaced by LOCF and the analysis will be performed for the PP population. Treatment differences between each abicipar group and ranibizumab and the corresponding 2-sided 95.1% confidence intervals for the difference will be calculated based on the least–square means and appropriate contrasts from the same ANCOVA model.

Tipping point analysis as described in Section 5.2.4.2 will be performed for BCVA change using the PP population. The tipping region will be constructed based on the combinations of values for δ_{2Q8} , δ_{2Q12} , or δ_{rQ4} that resulted in a lower bound of the 95.1% CI for the difference of abicipar (2Q8 or 2Q12) minus ranibizumab less than -5 letters.

5.3.2 SD-OCT CRT Mean Change from Baseline

The electronic SD-OCT images will be evaluated and graded by the Fundus Photograph Reading Center (FPRC). The graded results will be captured on the evaluation form and used for statistical analysis. In the event of excess fluid at baseline and ungradable images that result in missing baseline CRT, the manual read data for retinal thickness at the center point, if available, will be used for analysis.

CRT is measured as the thickness of the subfields, which is the central 1000 μ m from the center of the fovea.

Analysis of CRT mean change from baseline in the study eye will be performed using the same MMRM model for superiority testing based on the ITT population as described in

Section 5.3.1 for the key efficacy variable of BCVA change. The only difference is that baseline CRT will be included in the model as a continuous variable instead of a dichotomy (eg, $\leq 400 \ \mu m$ or $> 400 \ \mu m$) as used for randomization.

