7.3.2 Secondary Efficacy Analyses

The secondary efficacy analyses will be performed at week 52 for variables listed in Section 7.2.2 using the ITT and PP populations.

For the key secondary efficacy endpoint (mean change from baseline in BCVA at week 52), the statistical analysis for the non-inferiority test will be based on the PP population [REDACTED]

[REDACTED]
[REDACTED]
[REDACTED]
[REDACTED]

[REDACTED] The difference in mean change from baseline in BCVA between each abicipar arm and ranibizumab (abicipar group minus ranibizumab group) and the corresponding 2-sided 95.1% CI will be calculated based on the MMRM model. The non-inferiority test will be performed using a non-inferiority margin of 5 letters. Non-inferiority of abicipar is established if the lower limit of the CI is > - 5.0 letters. The same [REDACTED] model will be applied to the ITT population and the lower limit of the CI will be compared to the 5-letter margin for non-inferiority testing and to zero for superiority testing.

As a sensitivity analysis, mean change in BCVA will be analyzed using an analysis of covariance (ANCOVA) model, which includes the treatment group, baseline CRT (≤ 400 or > 400 microns), and lesion type of choroidal neovascularization (predominantly classic versus minimally classic or occult) as fixed effects and baseline BCVA as a covariate.

For the analysis of secondary efficacy variables, change from baseline in CRT and change from baseline in NEI-VFQ-25 composite scores, similar analysis procedure will be used as outlined for BCVA above for superiority testing using the ITT population.

For the secondary efficacy endpoint, proportion of patients with a gain of 15 or more letters, a similar analysis procedure will be used as outlined for the primary efficacy variable of stable vision for superiority testing using the ITT population.

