5.3.4 NEI-VFQ-25 Mean Change from Baseline in Composite Score

The NEI-VFQ-25 will be administered at the Baseline/Day 1, and at Weeks 12, 24, 36, 52, 76, and 104/early exit visits. Detailed analyses and analysis visit windows are described in Section 7 for health outcome data analysis.

As a secondary efficacy variable, change from baseline at Week 52 in the overall composite score will be analyzed for superiority testing using the ITT population and MMRM as described in Section 5.3.1 for the key secondary efficacy variable of BCVA change. The model will include the treatment group, region, baseline BCVA in the study eye, baseline VFQ score, visit, and treatment-by-visit interaction as fixed covariates using an unstructured covariance matrix. Treatment differences and the corresponding 95.1% confidence intervals will be constructed using the MMRM model.

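### As written, the CRT model lets the baseline-BCVA slope vary by visit but holds the baseline-CRT slope constant, which can cost a little precision at Week 52

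*SAP*

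**What the plan says.** SAP 5.3.1 defines the mixed model for repeated measures (MMRM) for BCVA change. Its terms are treatment, region, baseline BCVA, dichotomised baseline CRT and lesion type, and then "visit, visit-by-baseline BCVA interaction, and treatment-by-visit interaction as fixed covariates using an unstructured covariance matrix". The outcome's own baseline therefore has a separate slope at each visit.

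SAP 5.3.2 applies this model to CRT change, for superiority in the ITT population, with one stated modification: "The only difference is that baseline CRT will be included in the model as a continuous variable instead of a dichotomy". The cross-reference fixes the whole CRT model, so this is not a gap left by redaction.

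SAP 5.3.4 lists the NEI-VFQ-25 terms separately. After treatment, region and baseline BCVA they are "baseline VFQ score, visit, and treatment-by-visit interaction as fixed covariates using an unstructured covariance matrix". There is no visit-by-baseline VFQ term.

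Protocol 7.3.2 is looser. For CRT and NEI-VFQ-25 it says only that a "similar analysis procedure will be used as outlined for BCVA above for superiority testing using the ITT population". In SAP Section 5 the CRT endpoint is "Mean change from baseline in CRT as assessed with SD-OCT and quantified by the central reading center at Week 52", listed as secondary; the key secondary endpoint is BCVA change.

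**The concern.** The device that protects the BCVA analysis, a visit-specific slope for the outcome's own baseline, did not carry over to CRT. It stayed attached to baseline BCVA, which in the CRT model is a different measurement, and no visible text explains why.

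A thick retina has more thickness to lose, so CRT change is likely to depend on baseline CRT, and that dependence could change as fluid clears. If it does, a slope pooled over visits is not the Week 52 slope. Two things could follow. Baseline-related variance stays in the Week 52 residual and widens the interval for the superiority comparison. And when Week 52 values are missing, the model's implicit prediction of them uses the wrong slope.

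**Working it through.** **The plan's own figure.** The documents give no power, SD or effect size for CRT. The only figure that can be reproduced is the primary-endpoint power in SAP 1.2. With 90% response in both groups, a 10% margin and 240 per arm, the standard error is √(2 × 0.09/240) = 0.0274, and power = Φ(0.10/0.0274 − 1.96) = 95.5%, against about 95% stated; 720/0.8 = 900. That agrees, and nothing below depends on it.

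**Interactions with visit, side by side.**

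| Model | Own baseline × visit | Baseline BCVA × visit |
|---|---|---|
| BCVA (5.3.1) | yes | yes (same term) |
| CRT (5.3.2) | no | yes |
| NEI-VFQ-25 (5.3.4) | no | no |

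**Formula.** Take complete data and a full treatment-by-visit term. The adjusted Week 52 difference is then the raw difference minus g times the between-arm difference in mean baseline CRT, where g is the pooled slope. Write b52 for the true Week 52 slope, SDx for the baseline SD and s for the Week 52 residual SD. Relative to visit-specific slopes:

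variance inflation = 1 + (b52 − g)² × SDx²/s²

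**Inputs.** From the documents: Week 52 contrast, 95.1% interval, 240 per arm, unstructured covariance. Assumed, because the documents do not give them: SDx, s, the slope path, the residual correlations and 13 CRT visits to Week 52. For the linear drifts below, g is the midpoint of the path.

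| Slope of CRT change on baseline, Week 4 to Week 52 | SDx / s (microns) | Distance of b52 from g | Inflation |
|---|---|---|---|
| constant | any | 0 | 0% |
| −0.65 at Week 4 only, then −0.85 | 120 / 70 | 0.015 to 0.055 | 0.1 to 0.9% |
| linear −0.75 to −0.85 | 120 / 70 | 0.05 | 0.7% |
| linear −0.65 to −0.85 | 120 / 70 | 0.10 | 2.9% |
| linear −0.55 to −0.85 | 120 / 70 | 0.15 | 6.6% |
| linear −0.7 to −0.8 | 110 / 60 | 0.05 | 0.8% |
| linear −0.6 to −0.8 | 110 / 60 | 0.10 | 3.4% |
| linear −0.5 to −0.8 | 110 / 60 | 0.15 | 7.6% |

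The last row is 1 + 0.15² × 110²/60² = 1 + 0.0225 × 3.361 = 1.076. With 110/60, paths that level off after the early visits give at most 4.7%, mostly below 2%. The SD ratio matters: the drift from −0.55 gives 2.8% with 100/90 and 14.6% with 140/55.

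**Interval width.** With s = 70 the 95.1% half-width is 1.97 × 70 × √(2/240) = 12.6 microns. The three 120/70 linear drifts make it 12.6, 12.8 and 13.0 microns.

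**Stratification.** SAP 1.1 stratifies randomisation on CRT (≤ 400 versus > 400 microns), which limits baseline imbalance. For a normal baseline with SD 110 and an assumed mean of 350 to 450 microns, 36 to 41% of the variance lies within strata, so the 7.6% falls to 7.6% × 0.36 to 0.41 = 2.7 to 3.1% in true variance. In a simulation (three arms of 240, five visits, complete data, 1,500 replicates per scenario), the model-reported variance ratio ranged from 1.00 to 1.12. The empirical ratio was at most about 1.10 with simple randomisation and 1.05 with stratified randomisation. No bias beyond simulation error appeared.

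**Dropout.** Large simulated samples were used: two arms, five visits, no true difference, and dropout of about 18% versus 19 to 22% that depended on baseline CRT in one arm only. The common-slope estimate differed from the visit-specific one by 1 to 2 microns (drift from −0.65) and 2 to 4 microns (drift from −0.5). With a constant slope the two agreed to within 0.02 microns. The visit-specific estimate stayed within 0.7 microns of zero.

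No calculation was made for NEI-VFQ-25.

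**The case against.** The model is prespecified, and a common slope is a legitimate choice. Every figure above rests on assumed SDs and slopes. All arms are dosed at baseline and Week 4, so a slope that settles early is at least as plausible as a drift lasting the whole year, and then the loss is mostly below 2%. Even 7.6% inflation takes a test with 80% power only to about 77%, and 2% takes it to 79.2%. With complete data a wider interval makes a superiority test conservative, and no primary or key secondary decision depends on it. All of this stands.

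A reader might infer that the model certainly loses precision. The documents do not support that: they contain no CRT slope at any visit, and a constant slope costs nothing. A reader might also turn the largest figure into an equivalent loss of about 7% of the patients. That takes an extreme drift as typical and ignores stratification on CRT. Nor can the CRT figures be carried over to NEI-VFQ-25, which has four post-baseline visits up to Week 52 and no stated slope or SD, and whose detailed analyses are deferred to a section not in the public text.

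What does not stand is the view that the effect is always conservative. With dropout related to baseline CRT differently by arm, the estimate itself can move. The documents anticipate about 20% dropout, and SAP 5.1 excludes efficacy data after non-study anti-VEGF treatment in the study eye, but nothing visible links missingness to baseline CRT.

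**Conclusion.** The reading of SAP 5.3.2 is exact: visit-by-baseline BCVA is kept, and baseline CRT has one slope for all visits. The consequence is conditional. If the Week 52 slope differs from the pooled slope, the analysis can lose some precision: typically 0 to 3% of variance, and about 7 to 8% for a large year-long linear drift. An extreme SD ratio would raise that and a constant slope makes it zero. The reported interval carries this inflation; the true loss is smaller because of stratification. A shift of a few microns needs both slope drift and arm-differential dropout related to baseline CRT, and is modest beside a half-width of about 12.6 microns.

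This is a minor, optional improvement to a non-key secondary analysis. It does not question the primary or key secondary conclusions, and with complete data it does not threaten type I error. One limit: the SAP supplied is labelled for study 150998-005 and the protocol for 150998-006, so the point concerns the SAP text, with which the visible protocol wording does not conflict.

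**What to change.** In SAP 5.3.2, list the CRT model terms explicitly. Include continuous baseline CRT and visit-by-baseline CRT, in place of or in addition to visit-by-baseline BCVA. Keep treatment, region, baseline BCVA, lesion type, visit, treatment-by-visit, the unstructured covariance and the Week 52 contrast. Alternatively, state why a common baseline-CRT slope is adequate.

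For consistency, add visit-by-baseline VFQ score in SAP 5.3.4. Its benefit is not quantified.

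The cost is SAP wording and no new data. Replacing the interaction uses about zero net degrees of freedom. Adding it uses one fewer than the number of post-baseline CRT visits (12 if there are 13 visits, an assumption); the VFQ term uses 4 − 1 = 3. Both are small against about 900 randomised patients. The change should be made before unmasking at the Week 52 database lock.
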